3.3 Endpoints

Primary Endpoint

To evaluate the adverse events occurring from Day 1 to Day 5 (including vital signs, physical findings, clinical laboratory, and electrocardiogram (ECG) results) as characterized by type, frequency, severity [as graded by the National Cancer Institute Common Terminology Criteria

for Adverse Events [CTCAE] version 5.0], timing, seriousness, and relationship to study therapy after administration of 200 mg QD, 200 mg BID and 400 mg BID for continuously 5 days to healthy subjects.

Secondary Endpoint

Changes in blood chemistry and other health assessments from Day 1, Day 3, Day 5, and Day 6 morning.

3.4 Data Monitoring Committee (DMC)

Throughout the trial, all safety and tolerability data will be reviewed and monitored by an independent DMC. The composition and functions of the DMC will be governed by a charter, which will be described elsewhere.

A DMC safety listing and table based on frozen cleaned data will be conducted by QPS-Qualitix. The DMC safety listing and table will be generated based on this SAP mock listing and table. (Refer to Appendix A and Appendix B)

4. GENERAL STATISTICAL ISSUES

In general, all summaries will be displayed by treatment group and overall, and if applicable. Unless otherwise noted, all summaries will be descriptive in nature and will include number of subjects (N) and number of events (E) if applicable.

4.1 Continuous endpoints

Descriptive statistics including number of observations, mean, median, standard deviation, minimum and maximum will be presented for the raw data as well as change from baseline. The mean and median will be presented with one more decimal than the original data; standard deviation will be presented with two more decimal than the original data; minimum and maximum values will be presented with the same precision as the original data. For the calculation of baseline corrected values, baseline is defined as the last information collected before dosing for each parameter.

4.2 Categorical endpoints

The count and percentages will be used to summarize the categorical data. Percentages with float will be presented with 2 decimals; percentages with divisible number will be presented with 0 decimal.

4.3 Sample size estimation

A total of 30 subjects will be assigned sequentially into 3 cohorts in this study. The sample size is based on clinical judgment. No statistical power calculation is used to establish the sample size for this proof-of-concept study.

5. DATA HANDLING PROCEDURES

5.1 Coding System

Medical coding includes AE coding, medical history coding and concomitant medication coding. AE coding and medical history will be coded by Medical Dictionary for Regulatory Activities (MedDRA) Version 25.1 or higher and concomitant medication will be coded by WHODrug Global, B3, September 2022 or the most updated version. The latest version before database lock (DBL) will be adopted for final analysis.

5.2 Missing Data Handling

For data listings, all raw data will be reported/ displayed exactly as provided. No imputation will be performed on missing data. All analyses will be performed on data available at the time point considered. In summary tables, the number of subjects without missing data will be presented unless otherwise specified. In calculations of percentages, subjects with missing data will not be considered in numerator or denominator unless otherwise specified.

6. ANALYSIS OF STUDY POPULATIONS

Intent-to-treat (ITT) Population

The ITT population is defined as all assigned subjects who received at least one dose of study drug. This population will be used as the primary analysis population for analysis of the primary and secondary endpoints.

Per-protocol (PP) Population

The PP population is defined as the set of subjects who meet the ITT population requirements and are not associated with any major protocol violations. This population will be identified before the database lock. This population will be used as the supportive analysis population for analysis of the primary and secondary endpoints.

Safety Population

The Safety population is defined as any subject receiving at least one dose of CX-4945. This population will be used for the analysis of safety parameters.

Because of primary/secondary endpoint equals to safety endpoint. If the subjects included in three populations are the same, all analysis tables will only be presented by safety population with a footnote explaining that all populations are the same. Otherwise, it will be analyzed by three populations.

7. DISPOSITION OF PATIENTS AND STUDY COMPLETION

Data on date of visit will be listed in Listing 16.2.1.1. Data on the completion status and primary reason for study discontinuation will be listed in Listing 16.2.1.2. The subject disposition and completion status will be summarized by treatment group in Table 14.1.1. The subject eligibility will be listed in Listing 16.2.1.3. All minor and major protocol deviation(s) will be listed in Listing 16.2.2. All subjects who excluded from ITT, PP and safety population will be listed in Listing 16.2.3.

8. DEMOGRAPHICS AND OTHER BASELINE CHARACTERISTICS

8.1 Demographics and Baseline Characteristics

Subject demographics will be listed in Listing 16.2.4.1. Subject height, weight and body mass index (BMI) collected at screening will be listed in Listing 16.2.4.7. Demographics and baseline characteristics including height, weight, BMI, medical history, prior and concomitant medications/therapies will be analyzed with descriptive statistics and summarized for ITT, PP and safety population by treatment group in Table 14.1.2.

8.2 Medical History

Medical history will be coded by MedDRA version 25.1 or higher and listed by subject in Listing 16.2.4.2.

8.3 Concomitant Medication

All concomitant medications will be coded by WHODrug Global, B3, September 2022 or the most updated version and listed in Listing 16.2.4.3 and be summarized by treatment group using the coded term and preferred name in Table 14.1.3. Concomitant non-medication therapies will be listed in Listing 16.2.4.4.

8.4 Anti-SARS-Cov2

Subject anti-SARS-Cov2 test collected on Day 1 will be listed in Listing 16.2.4.5.

8.5 Serology

Clinical laboratory analyses serology test collected at Screening will be listed in Listing 16.2.4.6.

9. EXTENT OF EXPOSURE AND DRUG COMPLIANCE

9.1 Study Drug Administration

The information of date and time of study drug administration will be listed in Listing 16.2.5.

- Table 14.3.1.5: Treatment-Emergent Adverse Events by Relationship to Study Drug - MedDRA
- Table 14.3.1.6: Treatment-Emergent Adverse Events by Action Taken with Study Drug - MedDRA
- Table 14.3.1.7: Treatment-Emergent Serious Adverse Events by Severity - MedDRA
- Table 14.3.1.8: Treatment-Emergent Serious Adverse Events by Relationship to Study Drug - MedDRA
- Table 14.3.1.9: Treatment-Emergent Serious Adverse Events by Action Taken with Study Drug - MedDRA
- Table 14.3.2.1: Listing of Subjects with Treatment-Emergent Serious Adverse Events

- Table 14.3.2.2: Listing of Subjects with Treatment-Emergent Adverse Events Leading to Premature Discontinuation
- Table 14.3.2.3: Listing of Subjects with Treatment-Emergent Adverse Events Leading to Death

10.2 Clinical Laboratory Tests

Clinical laboratory analyses including hematology, blood biochemistry, urinalysis, microscopic exam, coagulation and serum/urine pregnancy test will be listed in Listing 16.2.8.1 through Listing 16.2.8.6.

All abnormal laboratory values and evaluation flags ‘NCS’ (not clinically significant) or ‘CS’ (clinically significant) will be listed in Table 14.3.4.

The observed results and the mean change from baseline of hematology, blood biochemistry, urinalysis and coagulation will be summarized by each testing parameter, each visit and group in Table 14.3.5.1 through Table 14.3.5.4. The shift tables of hematology, blood biochemistry and urinalysis will be provided by each testing parameter, post baseline visit and group in Table 14.3.5.5 through Table 14.3.5.8.

For any laboratory results reported as “<limit of quantification (<LLOQ)”, the numeric value used for summary will be the half of LOQ value. For results reported as “>limit of quantification (>ULOQ)”, the numeric value used for summary will be the LOQ value plus one unit of the minimum digits of the parameter. For example, if the results is “> 2”, the numeric value will be 2 plus 1 which is 3; if the results is “< 0.5”, the numeric value will be half of 0.5 which is 0.25.

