- [9] Urine samples will be tested for color, appearance, specific gravity, pH, protein, glucose, occult blood, ketones, leukocyte esterase, nitrite, bilirubin, urobilinogen, and microscopic examination of urine sediment.
- [10] In response to the COVID-19 pandemic, the subject will need to follow the currently site's policies for COVID-19 to get the negative results of anti-SARS-CoV2 test before admission.

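### The half-LOQ rule in SAP 10.2 exempts no parameter; if urine specific gravity is ever reported as '<x', it gives an impossible value that distorts the cohort mean

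*SAP*

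**What the plan says.** SAP 10.2 gives one substitution rule for each end of the reporting range. Its scope is general: it opens with "For any laboratory results reported as" and names no exception. Below the lower limit, "the numeric value used for summary will be the half of LOQ value"; above the upper limit, the value is "the LOQ value plus one unit of the minimum digits of the parameter". The worked example for the lower rule is a result of '<0.5', where "the numeric value will be half of 0.5 which is 0.25".

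The same section states that the observed results and the "mean change from baseline of hematology, blood biochemistry, urinalysis and coagulation will be summarized by each testing parameter", at each visit and in each group. For urinalysis this is Table 14.3.5.3, which SAP Appendix B marks for the DMC. Footnote [9] to the schedule in SAP 3.2 defines the urinalysis panel: "Urine samples will be tested for color, appearance, specific gravity, pH", followed by the other dipstick items and the sediment examination. SAP 4.1 adds that continuous data are shown with mean, median, SD, minimum and maximum, for raw values and for change from baseline.

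Nothing elsewhere in the SAP narrows the rule. SAP 5.2 rules out imputation, but for missing data, and a '<x' result is not missing.

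**The concern.** Half the limit is a defensible stand-in when the true value lies somewhere between zero and the limit. That is the position for a concentration such as the one implied by the SAP's own example. It is not the position for specific gravity, which is a ratio to water and for urine does not fall to half the density of water. Nor is it the position for pH, where half of a logarithmic value has no measurement meaning.

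The upper rule does not share the problem: '>1.030' would become 1.031 and pH '>9.0' would become 9.1, both sensible. Only the lower rule misbehaves for these two parameters.

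What is at stake is one descriptive table. Protocol 9.2.1 lists urinalysis changes among the safety measures, and they arguably fall under the other health assessments of the secondary endpoint. Protocol 9.7.4 plans no inferential statistics, so the descriptive tables are the analysis. With 10 subjects per cohort (SAP 3.1), one wrong value carries a weight of one tenth in the mean.

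**Working it through.** **The plan's own figures.** 0.5 / 2 = 0.25 and 2 + 1 = 3. Both worked examples in SAP 10.2 reproduce exactly.

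**Inputs from the documents.** Cohort size 10 (SAP 3.1); lower rule L/2 and upper rule L plus one unit (SAP 10.2); mean, median, SD, minimum and maximum for values and changes (SAP 4.1).

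**Assumptions, not in the documents.** Specific gravity: reporting limit L from 1.001 to 1.010, the other nine subjects averaging 1.015, between-subject SD 0.005 to 0.010. pH: limit 4.5 to 5.5, the other nine averaging 6.0, SD 0.5 to 1.0. One censored result per cohort unless stated.

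**Cohort mean.** With nine subjects averaging m, the mean under the SAP rule is (9m + L/2)/10. If the limit itself were used, it would be (9m + L)/10. The difference is -(L/2)/10, whatever m is.

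| Reported result | Substituted value | Mean, SAP rule | Mean, limit used | Shift |
|---|---|---|---|---|
| Specific gravity <1.001 | 0.5005 | 0.9636 | 1.0136 | -0.0501 |
| Specific gravity <1.005 | 0.5025 | 0.9638 | 1.0140 | -0.0503 |
| Specific gravity <1.010 | 0.5050 | 0.9640 | 1.0145 | -0.0505 |
| pH <4.5 | 2.25 | 5.625 | 5.85 | -0.225 |
| pH <5.0 | 2.50 | 5.650 | 5.90 | -0.250 |
| pH <5.5 | 2.75 | 5.675 | 5.95 | -0.275 |

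For '<1.005', for example: (9 × 1.015 + 0.5025)/10 = 9.6375/10 = 0.96375.

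**Shift against the assumed spread.** Specific gravity: 0.050/0.010 = 5 to 0.050/0.005 = 10 SDs. pH: 0.225/1.0 = 0.23 to 0.275/0.5 = 0.55 SD. Three censored pH results would shift the mean by 0.68 to 1.65 SDs.

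**Cohort SD.** If the other nine have SD s and the tenth value lies d from their mean, then SD² = (8s² + 0.9d²)/9.
- Specific gravity '<1.005', SAP rule: d = 1.015 - 0.5025 = 0.5125, so SD = 0.162 for s anywhere from 0.005 to 0.010.
- Same result, limit used: d = 0.010, so SD = 0.006 to 0.010.
- pH '<5.0', SAP rule: d = 3.5, so SD = 1.20 to 1.45. Limit used: d = 1.0, so SD = 0.57 to 0.99.

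**Change from baseline.** A subject who goes from 1.015 to '<1.005' shows 0.5025 - 1.015 = -0.5125 under the SAP rule, and -0.010 if the limit is used. Divided by 10, the contribution to the cohort mean change is -0.051 against -0.001. If the censored result is the baseline, the sign reverses and the error recurs at every later visit, because the same baseline is subtracted each time. For pH, 6.0 to '<5.0' gives -3.5 against -1.0, or -0.35 against -0.10 in the cohort mean change.

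**Median.** In these examples it is the same whether L/2 or L is used, because the censored result is the lowest value either way.

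**The case against.** The strongest reply is that the trigger may never occur. Protocol 8.2.1.4 sends samples to the site's local laboratory, and neither document gives a reporting limit for specific gravity or pH or says that either is reported as '<x'. A dilute urine reported as a plain number is not substituted at all. This stands: a reader might infer from the rule that impossible values will appear, and the documents support only that they would appear if such a result is reported. But a censoring rule is written for results that may occur, so this limits the importance of the point, not its correctness.

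A reader might also take pH to be as badly affected as specific gravity. It is not. A pH of 2.5 exists on the scale, and one such result moves the mean by about a quarter to a half of an assumed SD.

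Third, a reader might conclude that a real change would be hidden. The documents do not support that. The median and minimum are printed beside the mean, and a minimum near 0.50 would be conspicuous. The substitution applies to summaries only, while listings show results as provided (SAP 5.2). The urinalysis listing (16.2.8.3), the abnormal-value table (14.3.4) and the urinalysis shift table (14.3.5.7) all go to the DMC as well.

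Finally, no stated decision rests on these means. The primary endpoint is adverse events, and the laboratory stopping criterion in Protocol 4.3 uses graded, related laboratory events. This also stands. Against it, Protocol Section 10 puts no statistician on the DMC, so it is better to keep an artefact out of its tables than to rely on someone spotting it.

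**Conclusion.** The point holds as a conditional drafting error. The lower-limit rule, read as written, covers parameters for which halving is wrong, and no other text overrides it.

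For specific gravity the conclusion does not depend on which limit near 1.00 is assumed: one censored result in a cohort of 10 shifts the mean by about -0.050, takes it below 1.000 when the others are near 1.015, gives an SD of about 0.16 and adds about -0.051 to the mean change in Table 14.3.5.3. For pH the rule distorts the mean by about 0.25 per censored result and roughly doubles the SD at the smaller assumed spread, but does not swamp the mean.

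All of this rests on the assumption that the laboratory reports the parameter as '<x', and on the assumed limits and spreads shown above. The primary adverse-event endpoint and the listings are unaffected, and the median and abnormal-value table largely or wholly so. The point is of modest weight, but worth correcting because the correction is simple.

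**What to change.** In SAP 10.2, limit the half-LOQ rule to concentration-type parameters with a true zero. For urine specific gravity and pH, substitute the limit minus one reporting unit, which mirrors the existing upper-limit rule, or the limit itself. The choice hardly matters: with '<1.005' the cohort mean is 1.0139 using 1.004 and 1.0140 using 1.005; with pH '<5.0' it is 5.89 using 4.9 and 5.90 using 5.0. Whichever is chosen should be stated. It is also worth asking the local laboratory how it reports the two parameters, since that settles whether the rule can ever be triggered.

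The cost is one sentence in the SAP and one programming condition. No new data are needed.

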10.3 Vital Signs

Vital signs will be listed in Listing 16.4.1. The observed vital signs and the mean change from baseline over each visit will be analyzed with descriptive statistics and summarized by group in Table 14.3.6.

10.4 12-Lead Electrocardiogram (ECG)

12-lead ECG will be listed in Listing 16.4.2. The observed 12-lead ECG and the mean change from baseline over each visit will be analyzed with descriptive statistics and summarized by group in Table 14.3.7.

10.5 Physical Examination

Physical examination will be listed in Listing 16.4.3. The counts and percentage of physical examination will be summary by group in Table 14.3.8.

11. COMPUTER METHODS

All statistical analyses will be conducted using SAS® software, Version 9.4 of the SAS System for Windows 10. Copyright© 2016 SAS Institute Inc. SAS and all other SAS Institute Inc. product or service names are registered trademarks or trademarks of SAS Institute Inc., Cary, NC, USA.

APPENDIX A TABLE OF CONTENTS OF LISTING

Section	Title	Included in DMC
Listing 16.2.1.1	Subject Disposition (Date of Visit)	V
Listing 16.2.1.2	Subject Disposition (Completion Status)	V
Listing 16.2.1.3	Subject Eligibility	
Listing 16.2.2	Protocol Deviation List	V
Listing 16.2.3	Subjects Excluded from Analysis	
Listing 16.2.4.1	Individual Subject Demographics	V
Listing 16.2.4.2	Medical History	
Listing 16.2.4.3	Prior and Concomitant Medications	V
Listing 16.2.4.4	Non Medication Therapy	V
Listing 16.2.4.5	Clinical Laboratory Tests - Anti-SARS-Cov2	V
Listing 16.2.4.6	Clinical Laboratory Tests - Serology	V
Listing 16.2.4.7	Individual Subject Height and Weight	
Listing 16.2.5	Study Drug Administration	V
Listing 16.2.7	Individual Subject Adverse Events	V
Listing 16.2.8.1	Clinical Laboratory Tests - Hematology	V
Listing 16.2.8.2	Clinical Laboratory Tests - Blood Biochemistry	V
Listing 16.2.8.3	Clinical Laboratory Tests - Urinalysis	V
Listing 16.2.8.4	Clinical Laboratory Tests - Microscopic Exam	V
Listing 16.2.8.5	Clinical Laboratory Tests - Coagulation	V
Listing 16.2.8.6	Clinical Laboratory Tests - Serum/Urine Pregnancy Test	V
Listing 16.4.1	Individual Subject Vital Signs	V
Listing 16.4.2	Individual Subject 12-Lead Electrocardiogram (ECG)	V
Listing 16.4.3	Individual Subject Physical Examination	V

APPENDIX B TABLE OF CONTENTS OF TABLE

Section	Title	Included in DMC
Table 14.1.1	Summary of Subject Disposition	V
Table 14.1.2	Summary of Subjects Demographics and Baseline Characteristics	V
Table 14.1.3	Summary of Prior and Concomitant Medications - WHODrug	
Table 14.3.1.1	Treatment-Emergent Adverse Events	V
Table 14.3.1.2	Treatment-Emergent Adverse Events - MedDRA	V
Table 14.3.1.3	Treatment-Emergent Adverse Events - MedDRA (Preferred Term over 10 % in Any Treatment Group)	V
Table 14.3.1.4	Treatment-Emergent Adverse Events by Severity - MedDRA	V
Table 14.3.1.5	Treatment-Emergent Adverse Events by Relationship to Study Drug - MedDRA	V
Table 14.3.1.6	Treatment-Emergent Adverse Events by Action Taken with Study Drug - MedDRA	V
Table 14.3.1.7	Treatment-Emergent Serious Adverse Events by Severity - MedDRA	V
Table 14.3.1.8	Treatment-Emergent Serious Adverse Events by Relationship to Study Drug - MedDRA	V
Table 14.3.1.9	Treatment-Emergent Serious Adverse Events by Action Taken with Study Drug - MedDRA	V
Table 14.3.2.1	Listing of Subjects with Treatment-Emergent Serious Adverse Events	V
Table 14.3.2.2	Listing of Subjects with Treatment-Emergent Adverse Events Leading to Premature Discontinuation	V
Table 14.3.2.3	Listing of Subjects with Treatment-Emergent Adverse Events Leading to Death	V
Table 14.3.4	Abnormal Laboratory Values	V
Table 14.3.5.1	Laboratory Values Over Time - Hematology	V
Table 14.3.5.2	Laboratory Values Over Time - Blood Biochemistry	V
Table 14.3.5.3	Laboratory Values Over Time - Urinalysis	V
Table 14.3.5.4	Laboratory Values Over Time - Coagulation	V
Table 14.3.5.5	Individual Subject Changes (Shift Table) - Hematology	V
Table 14.3.5.6	Individual Subject Changes (Shift Table) - Blood Biochemistry	V
Table 14.3.5.7	Individual Subject Changes (Shift Table) – Urinalysis	V
Table 14.3.5.8	Individual Subject Changes (Shift Table) - Coagulation	V

QPS-Qualitix Clinical Research
Statistical Analysis Plan

CONFIDENTIAL
Protocol No.: CX4945-AV04-phase I
SAP Version: 1.0

Table 14.3.6	Summary of Vital Signs	V
Table 14.3.7	Summary of 12-Lead Electrocardiogram (ECG)	V
Table 14.3.8	Summary of Physical Examination	V
